## Phase II

After enrollment is completed for the in-person cohort (Phase I), we will enroll up to 5000 participants in a virtual cohort where there will be no in-person data collection. Participants will be recruited similarly to phase I, with 1) direct marketing; 2) community forums; 3) social media, 4) snowball recruitment and; 5) community organizations. Those who respond to study advertisements will take an eligibility survey via Qualtrics, consent and complete a baseline questionnaire. Eligible participants will be randomized via Prompt and receive the same 6-month iOTA-based intervention.

Since phase II participants will not come in for in-person follow-up assessments, participants will send us picture of their feet on a scale, with the weight visible wearing only light clothing with empty pockets and no shoes at 3-, 6- and 12-months.

### **3. Risks and Benefits**

This is a minimal risk study, and thus we do not anticipate problems beyond our control that involve risks to subjects.

Physical activity: Risks from increased physical activity will be minimized by: 1) recommending physical activity in line with national guidelines; 2) encouraging moderate activity; and 3) directing participants to their physicians when appropriate. If exercise-related symptoms are reported, we will advise participants to get clearance from their PCPs before they can restart physical activity.

Participants will be counseled to change behaviors that will maintain or reduce weight. If individuals follow this advice and decide to change their health behaviors, there should be few risks or side effects. The materials and counseling will provide guidance on preventing and managing the side effects of health behavior change.

Data confidentiality: We will use the standard operating procedures that have been used on our prior trials for survey conduct and data management. These procedures have been developed and used in many studies and we will adhere to these procedures for the proposed study. All paper files related to the study will be stored in a secure location at Duke University in a locked file cabinet accessible only to key study personnel. The privacy, security, and durability of accumulated personal health information are of paramount importance. Our existing practices

physical access to computing resources (hard drives, servers, networking equipment) is secure, audited, and restricted to skilled personnel; virtual access (login and system administration) is encrypted, audited, and limited to skilled personnel; all databases are encrypted and access from the public Internet is precluded; all software and servers are reachable only via a virtual private network (VPN); and all interface (API) and third-party software is encrypted using SSL. Personnel will have access to perform regular maintenance duties. However, this constituency is limited to senior system administrators and the director of the research group.

Breach of confidentiality: All participant information collected in the context of this study, and even the fact that an individual is participating in the study, will be considered confidential. Confidentiality will be assured through several mechanisms. First, each participant will be assigned an anonymous study ID that will be used on all study forms. Second, all study forms

and paper records that contain participant information (e.g., address lists) will be kept in secured, locked areas or in encrypted databases. In addition, such materials, when in use, will be kept away from public scrutiny. Materials that need to be discarded will be destroyed. Third, access to all participant data and information will be restricted to authorized personnel. In the case of computerized study data, access to data will be password protected and staff members will be assigned individualized passwords that allow them access to only those elements of the data management system to which they are authorized. In addition, all study personnel will maintain certification with the Duke IRB that they have completed training in research ethics, which includes training on confidentiality. Finally, participants will not be identified by name in any reports or publications, nor will data be presented in such a way that the identity of individual participants can be inferred.

All information obtained in the course of the study that identifies an individual will be treated as confidential in accordance with section 903C of the Public Health Service Act (42 U.S.C.299a-1). We will strip all identifiers from analytic data sets after data merging and will keep all personal identifiers in a separate location from the analytic data. No individual participant will be identified in any reports from the study. Data storage will involve computer files that will be password protected and encrypted and will be accessible only to personnel who need to contact participants.

Study surveys, including the online eligibility screen, will be administered using Qualtrics. We will deliver separate surveys to participants in order to minimize drop off and maximize participant security. Each participant will be asked to fill out one survey with his or her name and contact information; participants will thereafter use only study ID or a unique link when completing surveys. At various timepoints throughout data collection and after, we will download survey data from Qualtrics for analyses. Data sets will be de-identified before being downloaded. Data will be downloaded using the Qualtrics export feature. Data will be

protected. A copy of the raw de-identified data set and/or the results of the analyses will be uploaded to a Box sensitive folder. When the study biostatistician is ready to analyze the data in SAS, a statistical analysis program. She will upload the de-identified data, and SAS will store a copy locally to work from. This data set will be deleted from SAS after analyses are completed.

In order to send and receive text messages, we will use a software engine designed by Duke software engineers, called Prompt. Prompt uses Twilio, Heroku, and Amazon S3. Prompt will receive self-monitoring data that participants send via text message. The data will be automatically analyzed each week according to algorithms we embed. Study staff will log into a password-protected database using multi-factor authentication to view and edit participant information. We will use Twilio to send text messages to participants each week. We delete data from Twilio at least every 2 weeks. We will use Heroku to process data for the engine. We will use Amazon S3 to store data; data will be encrypted when it is stored. If these companies or their business partners disclose data, it may no longer be covered under the Duke privacy protections. Text messaging does not provide a completely secure and confidential means of communication. Participants will be made aware of these risks as well as those that are inherent in using text messaging during the informed consent process. We have used these processes on several previous studies conducted in this population.

Potential Benefits: Potential benefits for study participants include improved lifestyle, lower weight and blood pressure and consequent reduction in cardiovascular risk. An additional benefit for some participants may be personal satisfaction in being part of a study that may have major public health implications for the community. No benefit from participation can be

guaranteed. Potential benefits to others include the possibility that this research will lead to the dissemination of an intervention that can help maintain weight, with consequent reduction in the risks associated with diagnoses of diabetes, high cholesterol, and hypertension. The minimal health risks to participants listed above are offset by the potential benefits to them and to society.

#### **4. Confidentiality**

In the present study, we will collect identifying demographic information including: names, addresses, telephone numbers, email addresses, age, gender, race/ethnicity, health insurance, education, income, employment, health status, and marital status. We will use the standard operating procedures that have been used on our prior trials for survey conduct and data management. All paper files related to the study will be stored in a secure location at Duke University in a locked file cabinet accessible only to key study personnel. The privacy, security, and durability of accumulated personal health information are of paramount importance. Physical access to computing resources (hard drives, servers, networking equipment) is secure, audited, and restricted to skilled personnel; virtual access (login and system administration) is encrypted, audited, and limited to skilled personnel; all databases are encrypted and access from the public Internet is precluded; all software and servers are reachable via a password-protected database that is enabled with multifactor authentication; and all communication (API) and third-party software is encrypted using SSL. Personnel must have access to these databases to perform regular maintenance duties. However, this constituency is limited to senior system administrators and the director of the research group.

Strategies for protecting electronic PHI: Screening, outcome measures (height, weight, sociodemographics) and surveys will be entered into Qualtrics and Redcap. We will also enter some participant information (phone number, study group, and behavioral goals) into a software engine developed by Duke software engineers. Prompt is developed on Heroku, a managed container system for data. We will use Heroku to process data analytics. All web-transmitted data are encrypted using a protocol called Transport Layer Security (TLS) or Secure Sockets Layer (SSL). This type of security is most often used for web sites that are doing eCommerce (selling products/services over the Internet). The reason for the increased security is to protect the privacy of visitors/customers and transmission of personal, confidential, financial or billing information over the Internet. We will also password protect study data on Prompt and use multifactor authentication processes. As described above, physical access to computing resources (hard drives, servers, networking equipment) is secure, audited, and restricted to skilled personnel; virtual access (login and system administration) is encrypted, audited, and limited to skilled personnel; all databases are encrypted and access from the public Internet is

(API) and third-party software is encrypted using SSL. Only research staff who have received CITI Certification and are listed on the Duke University Institutional Review Board protocol will have access to the study database. Information in the database will not be shared with anyone outside the research team. On the study consent form (Appendix A), we inform participants that we do collect identifying information and that we take all appropriate measures to minimize the risk of unintentional breach of confidentiality.

The information generated by this study will be kept for seven years after the date of last publication. Then it will be destroyed by shredding the paper copies and by securely deleting the computer files.

Data management will take place under the supervision of [name]. Our group has developed extensive quality assurance procedures, including on-going quality control checks.

Some participants will choose to be reimbursed with an electronic Amazon gift card. Participants who choose this method of compensation will be asked to provide their email address, so we can email the gift card to them. Their email address will be stored in a password-protected, encrypted study database. They will not need to provide their social security numbers.

After data analysis, we plan to disseminate the results of the study via journal publications and presentations.

We will not collect information about illegal activities. Further, we do not expect that participants will reveal information subject to reporting because our coaches are instructed to maintain close adherence to a protocol that involves discussing only behavior change efforts related to diet and exercise.

## **5. Compensation**

Participants will be reimbursed in the form of an electronic Amazon gift card for their time at each of the evaluation visits: baseline, 3, 6, and 12 months (20,25,25,30 respectively). If a participant is determined to be ineligible at the time of the screening baseline visit, s/he will be compensated \$10 amazon e-card for his or her time. Participants who complete all 3 follow-up evaluation visits after baseline will be reimbursed an additional \$15 amazon e-card at his/her 12-month visit.

If a participant does not wish to provide their social security or tax identification number, they can be reimbursed using an electronic Amazon gift card for each visit. Participants who choose this method of compensation will be asked to provide their email address, so we can email the gift card to them. Their email address will be stored in a password-protected, encrypted study database.

## **6. Informed Consent**

Please see the consent form attached (Appendix A).

## **7. Deception**

Deception will not be used in the present study.

## **8. Debriefing**

We do not anticipate a need for debriefing.

## ***STATISTICAL ANALYSIS PLAN (SAP)***

# 1 Study Overview

Background/Introduction:

## 1.1 Study Aims

- Determine the effect of each of the five intervention components on absolute weight change from baseline to 6 months.
- Assemble a multicomponent treatment package including the comparator level of components with standardized main effect sizes of  $\geq 0.7$  kg. Otherwise, include the default level, unless interactions of  $\geq 0.7$  kg are present that would cause us to include the comparator level.

# 2 Study Population

## 2.1 Inclusion Criteria

- English language proficiency
- BMI above 25 kg/m^2
- Own a smartphone
- Be willing to receive multiple text messages daily.
- We aimed to recruit a sample that is 30% male and 40% racial/ethnic minorities.

## 2.2 Exclusion Criteria

- Exclusion criteria include the following conditions: prior or planned bariatric surgery; psychiatric hospitalization in past 12 months; pregnancy, nursing, or planned pregnancy; history of a cardiovascular event; history of an eating disorder; history of a condition (e.g., end stage renal disease, cancer, schizophrenia) or use of medications (e.g., lithium, steroids, anti-psychotics) that would affect weight measurement, for which weight loss is contraindicated, or might promote weight change; current participation in a weight loss trial and/or recent weight loss  $> 10\%$ , and; investigator discretion for safety reasons.

## 2.3 Sample size

Sample size: We plan to recruit 448 males and females aged 18-65 years who have English language proficiency, and a BMI between 25-40 kg/m^2. We plan to recruit a sample that is 30% male and 40% racial/ethnic minority.

Using the FactorialPowerPlan SAS Macro, we computed the sample size needed for a full 2x2x2x2x2 factorial design. We expect a minimal difference between groups, defined as an effect size of 0.15. With a standard deviation estimate from a recent weight loss trial of 5 kg, and a within-participant correlation of 0.9, this translates into a 0.75 kg difference in weight loss at 6 months between groups given the comparison level of the intervention component and those groups with the default level of the intervention component (main effects). We determined that a total sample size of 282 subjects would be required to achieve an overall power of 80% to detect a 0.75 kg difference in weight loss. We conservatively assume 30% dropout at 6 months, so we inflate the sample size to 403. To obtain an equal number of participants in each treatment combination (condition), we further inflate this sample size to 448, which is a final sample of 14 participants in each of the 32 conditions. The main effects are then estimated with 224 participants receiving either level of each component. Likewise, pairwise interactions are based on comparisons of means for 224 participants who receive both or neither component compared to those who received only one.

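### The 5 kg SD behind N=282 is not defined; the stated 80% power holds only if it is the SD of body weight at one visit, which is implausible here, and if it is the SD of weight change, power is about 24–26%

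*Combined protocol and SAP*

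**What the plan says.** SAP 2.3 starts from a standardised effect: "We expect a minimal difference between groups, defined as an effect size of 0.15". It then takes an SD from a recent weight loss trial "of 5 kg, and a within-participant correlation of 0.9, this translates into a 0.75 kg difference in weight loss at 6 months" for each main effect. From this it concludes that "a total sample size of 282 subjects would be required to achieve an overall power of 80% to detect a 0.75 kg difference". Dividing by 0.7 for dropout gives 403, which is rounded up to 448, or 14 in each of 32 conditions.

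The sample-size paragraph in protocol section 2 uses the same inputs and the same 282 and 403, but ends at up to 700. The calculation is attributed to software ("Using the FactorialPowerPlan SAS Macro"), without the inputs entered. Neither paragraph says what the 5 kg is the SD of, and no alpha or sidedness is given.

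The population is men and women aged 18–65. SAP 2.3 gives "a BMI between 25-40" kg/m². Protocol section 2 and SAP 2.1 require BMI above 25 with no upper limit. The primary outcome (SAP 3.1) is absolute weight change from baseline to 6 months.

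**The concern.** The precision of a comparison of weight change depends on the SD of change. Body weight varies far more between people than weight change does, and the two SDs are linked through the within-participant correlation. A correlation of 0.9 belongs in the calculation only if 5 kg is the SD of weight at a single visit. If 5 kg is already the SD of change, the correlation is built into it, and applying it again shrinks the SD a second time. The first reading needs an implausibly homogeneous sample; the second removes the stated power.

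This is the plan's only power statement. SAP section 4 assembles the intervention package from a 0.7 kg cut-off together with significance, so anyone weighing a retained or rejected component will rely on the 80%. If the SD of change is near 5 kg, real effects of the design size would usually be non-significant, and components with no effect would often pass the cut-off by chance.

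**Working it through.** **Inputs.** Difference 0.75 kg (0.15 × 5), SD 5 kg, correlation r = 0.9, power 80%, N = 282, dropout 30%, planned N = 448, all from SAP 2.3. Each main effect compares two equal halves of the sample, so SE = 2 × SD / √N. Alpha 0.05 two-sided is assumed.

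**1. Reproducing 282.** Treat 5 kg as the SD of weight at one visit.
- SD of change = 5 × √(2 × (1 − 0.9)) = 2.236 kg.
- Normal approximation: N = 4 × (1.96 + 0.842)² × 2.236² / 0.75² ≈ 279, so 140 per level, 280 in total.
- With the t distribution, N = 282 and power is 80.1%. The result is 282 whether 2, 16 or 32 model parameters are allowed for.
- 282 / 0.7 = 403, as stated.

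The other settings tried do not give 282:

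| Setting | N for 80% power |
|---|---|
| Baseline-adjusted SD, 5 × √(1 − 0.81) = 2.179 kg | 266–268 |
| SD 2.236 kg, one-sided 0.05 (or two-sided 0.10) | 220–222 |
| SD 2.236 kg, two-sided 0.025 | 338–341 |
| SD 2.236 kg, two-sided 0.01 | 416–419 |
| 5 kg used directly as the SD of change, two-sided 0.05 | 1,396–1,398 |

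On the 2.236 kg scale, 0.75 kg is 0.75 / 2.236 = 0.34 SD of change. It is 0.15 only of the 5 kg.

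**2. Is 5 kg credible as an SD of body weight?** The documents give no weight or height distribution, so heights are assumed.
- At a single height of 1.70 m, BMI 25–40 runs from 25 × 1.70² = 72 kg to 40 × 1.70² = 116 kg. A 5 kg SD would need a BMI SD of 5 / 1.70² = 1.7 with no variation in height.
- With 30% men, mean heights of 1.76 m (men) and 1.63 m (women) and height SDs of about 7 cm, height alone gives a weight SD of about 9.6 kg with BMI fixed at 32.
- Adding BMI variation (mean 32, SD 2 to 5, truncated to 25–40) gives 11–14 kg overall and 9–13 kg within gender.
- A change SD of 5 kg with r = 0.9 implies a weight SD of 5 / √0.2 = 11.2 kg, which fits this range.

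**3. Power if 5 kg is the SD of change.**

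| Completers | SE (kg) | Power for 0.75 kg |
|---|---|---|
| 282 | 0.595 | 24% |
| 314 (70% of 448) | 0.564 | 26% |
| 448 (no dropout) | 0.472 | 35% |
| 490 (70% of 700) | 0.452 | 38% |
| 700 (no dropout) | 0.378 | 51% |

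The difference detectable with 80% power at 314 completers is 2.80 × 0.564 = 1.58 kg.

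**4. Sensitivity at 314 completers.**
- Change SD of 3, 4, 5 and 6 kg: power 60%, 38%, 26% and 20%.
- Weight SD of 10, 12 and 15 kg with r = 0.9: change SD 4.5, 5.4 and 6.7 kg; power 32%, 23% and 17%.

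**5. The 0.7 kg cut-off.** With SE 0.564 kg, a component with no effect gives an estimate of at least 0.7 kg in one direction or the other about 21% of the time (0.7 / 0.564 = 1.24). With the SD behind 282, SE at 314 is 0.252 kg and the figure is about 0.6%.

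**The case against.** The arithmetic is not at fault: 282 follows from the inputs on one reading. A reader might go further and infer that the BMI criterion rules out a 5 kg weight SD, or that 5 kg must be the SD of change so that 26% is simply the trial's power. The documents support neither. An eligibility range does not fix an SD, the plausibility argument rests on assumed heights, and the cited trial's SD is not described. Nor does 0.15 × 5 = 0.75 settle the matter, because the product is the same whichever SD the 5 kg is. These points stand, and every replacement figure is conditional for that reason. A still lower power, near 11–12%, would need a weight SD of about 20 kg, for which the documents give no basis.

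It can also be said that SAP section 4 plans a baseline-constrained mixed model rather than a t-test in completers, and that the protocol allows up to 700 participants. Neither restores 80%. With a weight SD of 11.2 kg and r = 0.9, the baseline-adjusted SD is 11.2 × √(1 − 0.81) = 4.87 kg, and power at 314 is about 27%. At 490 completers with a change SD of 5 kg it is 38%.

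Finally, selection rests partly on a point estimate of at least 0.7 kg, so a non-significant result does not by itself decide a component's fate. That is fair, but the cut-off is also sensitive to the SE, as step 5 shows. SAP 2.4 dates the data transfer to November 2019, so the correction concerns what is reported, not the design.

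**Conclusion.** The concern holds in conditional form. The 80% at N = 282 depends on 5 kg being a single-visit SD of body weight, and that is not plausible for this population. On the readings examined with plausible inputs, power for 0.75 kg at 314 completers is well below 80%: about 26% if 5 kg is the SD of change, 32% to 17% for weight SDs of 10–15 kg with r = 0.9, and 60% even if the SD of change were as low as 3 kg. If 5 kg is the SD of change, 80% power would take about 1,398 completers.

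These figures assume two-sided alpha 0.05, equal halves for each main effect and, for the weight SD, the heights given above. The exact match to 282 supports the alpha but does not prove it. What the 5 kg measures is for the sponsor to confirm. Because the power figure is relied on and does not hold under plausible inputs, it should be corrected.

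**What to change.** In SAP 2.3 and the sample-size paragraph of protocol section 2:

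1. Confirm from the cited source what the 5 kg is the SD of, and say so. Give the source of the 0.9.
2. State alpha, sidedness and the inputs entered in the macro.
3. Use either an SD of 6-month change with no further correlation adjustment, or a realistic SD of body weight with a matching correlation. The pooled SD of 6-month change, computed without reference to component levels, can settle the value.
4. Replace the statement of 282 subjects for 80% power with the power and detectable difference at the planned number of completers. If 5 kg is confirmed as the SD of change, at 314 completers that is about 26% for 0.75 kg and 80% for about 1.6 kg.

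The cost is a rewritten paragraph in each document and, in all likelihood, a less favourable stated power. Enrolment, intervention and planned analysis do not change.
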